## **9.2 Trial Performance**

### **9.2.1. Treatment Intervention Integrity**

There are two primary threats to the integrity of the interventions. First, the therapists may not deliver the interventions as intended. Important material may be left out or provided incorrectly. Two procedures will be employed to minimize this potential problem. Both interventions (HIV/AIDS Education and REMAS) will be manual driven, and the therapists will receive approximately 20 hours of training in conducting the interventions. All intervention sessions will be audio taped. The lead investigator, or the node investigator, or the node project coordinator for the protocol will review twenty percent of each therapist's tapes. Therapists will receive feedback on deviations from the manual. Section 6.3.3. provides additional details on maintaining treatment intervention integrity.

The second potential threat to intervention integrity is contamination between the interventions. Since the HIV/AIDS Education material is a subset of the REMAS intervention there is not a concern regarding HIV Education material contaminating the REMAS intervention. However there is a concern that HIV/AIDS Education participants may be exposed to REMAS intervention material in one of three ways. Since therapists will be trained to deliver both interventions there is a concern that the therapists will deliver REMAS unique materials when providing the HIV/AIDS Education intervention. Participants in the REMAS intervention group will share REMAS unique material to HIV/AIDS Education group participants. Finally HIV/AIDS Education participants may be provided REMAS unique material from sources the investigators will not be in a position to control. These include media, campaigns, street outreach workers and substance abuse counselors not associated with the study. Both of the procedures described above will help to lessen contamination problems (audio taping and supervision). Three additional procedures will be in place to maintain the integrity of the interventions. The design of the HIV/AIDS Education session leaves little room to add additional information, and there is no time for role plays and brainstorming that characterizes the REMAS condition. At the end of each session interventionists will complete a checklist of the topics and activities to be covered in the session. To further ensure integrity, however, study participants will be asked to complete an intervention fidelity questionnaire at post-intervention and at each follow up assessment to determine if they have been exposed to elements of both the intervention to which they were assigned and not assigned.

### **9.2.2. Data integrity**

The Washington Node Data Management Center (DMC) will coordinate data management activities and be responsible for data integrity over-site. Please refer to sections 15.0 to 15.5 for more details of the data management plan. In addition the DMC will be responsible for ensuring the randomization procedures described in sections 6.3.1 and 4.0 are implemented and maintained correctly.

The CTN DSMB will review demographic characteristics of participants in each intervention condition to determine the efficacy of the randomization procedures. The CTN DSMB will review recruitment and retention data to determine the feasibility of the trial.

## **9.3 Trial Efficacy**

Given the absence of strong evidence supporting the impact of this intervention within a drug abuse treatment setting, we will plan to conduct an interim analysis, primarily for utility. See section 11.9 starting on page 39 for details of the interim analysis plan.

## **10.0 DEPARTURES FROM PROTOCOL**

All departures from protocol will be documented following appropriate CTN SOP forms, as well as Node-specific IRB reporting requirements.

## **11.0 STATISTICAL ANALYSIS**

### **11.1 Objectives of Analysis**

The proposed trial is intended to test the effectiveness of the REMAS intervention, as compared to that of a single HIV/AIDS education session, on the primary outcome, the number of unprotected vaginal and anal intercourse acts. Other secondary outcomes will include: frequency of “outer course,” number of sexual partners, possessing condoms, taking (male and female) condoms from open clinic supplies, attitudes towards condoms, gender role beliefs, and frequency of using drugs with sex.

### **11.2 Primary Outcome and Statistical Hypotheses**

There is one primary outcome measure, the number of unprotected vaginal and anal intercourse acts during the three month and six month follow up periods. This measure was used in Project Light (NIMH Multisite HIV Prevention Trial Group, 1998). The primary analyses will test the hypothesis that compared to single-session HIV/AIDS education participants, REMAS participants will significantly decrease their involvement in unprotected vaginal and anal intercourse from baseline assessment to follow up assessments. Intervention effects of secondary efficacy measures of interest will also be tested. We hypothesize that compared to the control group, the experimental group will have fewer sexual partners, engage in more “outer course,” demonstrate an increase in frequency of possessing condoms, in the likelihood of taking condoms from clinic stocks, positive attitude toward condom use, and egalitarian sex role beliefs; and a decrease in the percentage of sexual events that include drug taking.

### **11.3 Sample Size and Statistical Power**

The design of this study is a stratified cluster randomization trial (Donner & Klar, 2000). The randomization will be within strata (participating CTP site). A cluster is the cohort of 3-8 patients. Within each participating CTP site, cohorts of patients will be randomly assigned to the intervention or control conditions. Our sample size calculation is based on a comparison of outcomes between the intervention and control group measured at 6-month follow-up. This design has a two-level hierarchical structure, cohorts and CTP sites, resulting in two levels of correlation among subject’s responses: correlation due to cohorts and correlation due to CTP sites. Since the planned analyses will be based on the method of generalized estimating equation (GEE), our sample size calculation will be based on the formula given by

Liu and Liang (1997). Since we do not have any information on the relative magnitude of the possible correlation due to cohorts within CTP sites and due to CTP sites, we assume an equal correlation structure.

We let  $Y_{ijk}$  be the frequency of unprotected vaginal and anal intercourse of the  $i$ th subject in the  $j$ th cohort of the  $k$ th CTP site measured at the 6 month follow-up time, where  $i = 1, \dots, I$ ,  $j = 1, \dots, 2m$ , and  $k = 1, \dots, K$ . Let  $x_{ijk}$  be the treatment assignment indicator for the  $i$ th subject in the  $j$ th cohort of the  $k$ th CTP site. Here  $m$  is the number of cohorts per condition within the same CTP site.

We propose the following linear model for correlated data for our sample size calculation (Liu and Liang, 1997):

$$Y_{ijk} = \beta_0 + \beta_1 x_{ijk} + \varepsilon_{ijk},$$

where  $\varepsilon_k = (\varepsilon_{11k}, \dots, \varepsilon_{I(2m)k})'$  has a multivariate normal distribution with mean zero and covariance matrix  $\sigma^2 R$ . Here the correlation matrix  $R$  contains 1 for its diagonal entries and  $\rho$  for off-diagonal entries. Here  $\sigma^2$  is the variance of  $\varepsilon_{ijk}$  and  $\rho$  represents the correlation between any two observations from the same cohort as well as the correlation between two observations from different cohorts within the same CTP site. Note that we assume that the correlation between two observations from the same cohort is the same as the one between two observations from different cohorts within the same CTP site. Under this linear model, to detect the effect size  $\Delta$  in the average number of unprotected vaginal and anal intercourse between the intervention and control conditions at the type I error  $\alpha$  with a power of  $1-\beta$ , we need the following number of cohorts per condition in the study:

$$m = 2(z_{1-\alpha/2} + z_{1-\beta})^2 \{1 + (I-1) * \rho\} / (I * (\Delta)^2),$$

where  $z_{1-\beta}$  is the  $(1-\beta)$ th percentile of the standard normal distribution. This formula is the same as Formula (5.1) in Donner and Klar (2000).

From the above formula, we see that to calculate a required sample size we need to determine the standardized effect size  $\Delta$ . We have estimated the effect size on the basis of clinically important intervention effects observed in prior studies. The NIMH Multisite HIV Prevention Trial Group (1998) used the number of unprotected vaginal and anal intercourse acts as a primary outcome measure in Project Light. They observed an effect size ( $\Delta$ ) of 0.29. Assuming that we have an intracluster correlation no greater than  $\rho$  of 0.01 and an average of 8 participants per cohort ( $I=8$ ), using the above formula we find that the number of cohorts per condition required to detect the effect size of 0.29 with a type I error rate of 0.05 and a power of 80% is:

$$m = 2 * (1.96 + 0.84)^2 * \{1 + (8-1) * 0.01\} / (8 * (0.29)^2) = 25,$$

Therefore, we would require a total of  $8*25=200$  participants per condition, resulting in the total of 400 subjects in the study. Assuming each CTP site can contribute up to 40 subjects, the required number of CTP sites is 10. If each CTP site can only contribute an average of 32 subjects, we would require a total of 12 CTP sites. If each CPT can only contribute an average of 28, we would need a total of 14 CPT sites. Therefore, if we can recruit 14 good CTP sites, we would require each site to contribute a total of 28 subjects.

The following table provides estimates of the number of cohorts sites needed based on the above formula as should the average cohort size be less than 8.

I	# of the required cohorts per conditions
7	29
6	33
5	39
4	49

To allow a possible attrition rate of 10%, we would require a total of 440 participants for the estimate based on I=8. The investigators recognize that sample size calculations are best estimates based on previously obtained data when available. The effect size and intracluster correlation variation can result in significant variation in the sample sizes needed to obtain adequate power. For example if the intracluster correlation is twice what we are estimating (0.02) the total number of participants needed is 216 per condition or 476 total participants with 10% attrition rate. We propose to enroll 560 participants into the study. We feel this will provide some “cushion” for possible attrition, difficulty recruiting at any one site, or under estimation of the intracluster correlation.

#### **11.4 Study Population**

The study will be carried out at 7 MMTPs and 7 ODF who can each provide an average of 40 sexually active men within a recruitment period of approximately 6 - 12 months.

#### **11.5 Demographic Profile**

The demographic and screening or, if applicable, baseline characteristics of the (respective) total samples at each key point in the course of the study will be described using frequency distributions and measures of central tendency. These populations include: total population screened, total eligible population, total consenting population, total randomized population, and total completer populations. At each key point, frequencies and central tendencies of participating participants versus non-participating participants will be compared. At each key point, reasons for ineligibility, refusal, and/or dropping-out will be documented, and frequency of these reasons will be obtained. Within the randomized sample, the characteristics of participants in each intervention condition will be described.

#### **11.6 Analysis of Primary Outcome**

The primary objective is to compare the effectiveness of REMAS, an intensive, 5 session, male-specific group HIV/AIDS intervention, to a standard single session HIV/AIDS education group. It is hypothesized that men provided REMAS will engage in fewer risky sexual behaviors as measured by the number of unprotected vaginal and anal intercourse acts than will men provided the standard intervention. It is also hypothesized that being non-monogamous in the prior six months, years of stimulant use, and the baseline frequency of unprotected vaginal and anal intercourse will be associated with the number of unprotected

vaginal and anal intercourse acts at follow up. These three covariates will be entered into the data analytic model described more fully below. All analyses will be performed using an ITT strategy consisting of all randomized participants. Since our data have two levels of the hierarchical structure, we will apply a marginal semi-parametric regression model to analyze the primary outcome.

Hypothesis 1: REMAS will significantly reduce the number of unprotected vaginal and anal intercourse at both at the 3 and 6 month follow-up times in comparison with the standard single HIV/AIDS education session.

To test this hypothesis, we let  $Y_{ijk}$  be the frequency of unprotected vaginal and anal intercourse of the  $i$ th subject in the  $j$ th cohort of the  $k$ th CTP site measured at the  $t^{\text{th}}$  follow-up time. Let  $z_{1ijk}$  be the treatment assignment indicator for the  $i$ th subject in the  $j$ th cohort of the  $k$ th CTP site. Here  $m$  is the number of cohorts per condition within the CTP site. To adjust for the possible imbalance between conditions on the baseline value, we include the baseline value as a covariate; let  $z_{2ijk}$  be the baseline frequency of unprotected vaginal and anal intercourse of the  $i$ th subject in the  $j$ th cohort of the  $k$ th CTP site. The other two covariates we plan to include in the model are (1)  $z_{3ijk}$ , a binary indicator on whether the  $i$ th subject in the  $j$ th cohort of the  $k$ th CTP site is non-monogamous in the six months prior to the baseline and (2)  $z_{4ijk}$ , years of stimulant use for the  $i$ th subject in the  $j$ th cohort of the  $k$ th CTP site. As noted by Sen (1997), analyzing change from baseline does not remove the baseline imbalance. Hence, we propose to model the absolute frequency at a particular follow-up time and include the baseline frequency value as a covariate in regression.

The following marginal model for outcome of count will be used to test this hypothesis:

$$(1) \quad \log E(Y_{ijk}) = \beta_0 + \beta_1 z_{1ijk} + \beta_2 t + \beta_3 z_{1ijk} * t + \gamma_1 z_{2ijk} + \gamma_2 z_{3ijk} + \gamma_3 z_{4ijk}$$

where  $t=0$  for 3 months post intervention and  $t=1$  for 6 months post-intervention.

Based on the assumed model (1), our main null and alternative hypotheses are governed by the regression parameters  $\beta_1$ ,  $\beta_2$  and  $\beta_3$ . For example,  $\beta_3 \neq 0$  indicates that over time the effects of the two study interventions are different;  $\beta_3=0$  corresponds to no difference in the effectiveness of the interventions over time. If  $\beta_3=0$ , the parameter  $\beta_2$  estimates the rate of change in the outcome measure from 3 to 6 months post-intervention in the two intervention groups, and the parameter  $\beta_1$  estimates the difference between the experimental and control intervention, which is the same at the two follow-up assessment times.

Since all covariates used in the model are baseline covariates, we can assume we have complete information on the covariates. A patient who drops out during the study will result in missing outcomes. To be able to deal with possible missing-data, we will use the multiple imputation technique combined with the standard Generalized Estimating Equation (GEE) method for the parameters in model (1),  $\beta = (\beta_0, \beta_1, \beta_2, \beta_3, \beta_4)$ . A similar method for handling missing covariates has also been proposed by Xie and Paik (1997). In this multiple imputation approach, a missing value of the outcome will be imputed using a Bayesian bootstrap method (Rubin, 1987; Xie and Paik, 1997) to obtain 5 imputed values, resulting in 5 complete-data sets. We will use the following steps in this multiple imputation scheme: (1) we will build a logistic regression model to predict the missingness for the outcome; (2) based on this model we will assign a propensity score for missingness for each case; (3) for each patient with a missing outcome (Y), its donor pool of patients having observed outcomes will

be found such that their assigned propensity scores are close to the assigned propensity score for the patient with the missing outcome; (4) for the missing value of Y for the patient, we will generate 5 imputation values from its donor pool according to the Approximate Bayesian Method (Rubin, 1987).

This multiple imputation method has been implemented by Solas (Statistical Solutions Ltd, 2001). For each complete-data set, we will apply the standard GEE method to get a pair of GEE estimates for  $\beta$  and its variance, resulting in 5 pairs. Then, according to Rubin's formula (Rubin, 1987), we will obtain the multiple-imputation estimate for  $\beta$  and its variance with associated p-value and 95% confidence interval.

Although the above method can handle both missing at random (MAR) and non-MAR missing data patterns, the validity of the method requires appropriately modeling the missing-data mechanism. To assess sensitivity of the conclusions on the assumed missing-data mechanism we will use both a parametric model (Robins et al, 1994; Scharfstein et al, 1999) and a non-parametric model (Wang et al, 1997).

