### **6.3.1. Randomization**

As stated in section 4.0, upon completing the baseline assessment participants admitted to the study will be placed into an open cohort of participants waiting for randomization. The cohort will close once there are 8 men in the cohort or four weeks has passed since the first subject was placed in the cohort, whichever comes first. Groups should contain a minimum of 3 participants. If fewer than 3 are recruited during the four weeks, the cohort will remain open until a third participant is recruited. Once closed the cohort will be randomly assigned to attend either the REMAS intervention or the one session standard educational intervention. Separate block randomization schedules will be developed for each CTP with the assumption that 6 cohorts will eventually be randomized. Thus if recruitment is brisk a CTP may end up overshooting their target of 40 participants and actually recruit up to 48 participants. If a CTP has not recruited 40 subjects after six cohorts have been randomized the following procedures will be implemented. If there are less than 29 participants recruited (thus groups are averaging less than 5 participants each) a new block randomization schedule for four cohorts independent from the block randomization for the initial six cohorts will be prepared.

Assuming recruitment rates do not change dramatically the CTP should end up recruiting between 40-48 participants. If between 29-35 participants have been recruited a new block randomization schedule for two cohorts independent from the block randomization for the initial six cohorts will be prepared. If 35 or more participants have been recruited the CTP will recruit one additional cohort which will be randomly assigned to one of the conditions independent of previous cohort assignments in that CTP. The above randomization scheme was chosen over randomizing individuals so that the time participants would need to wait before being provided the intervention would be a maximum of 4 weeks after baseline assessment. With randomizing individuals an extended period of time might pass before enough participants to conduct the intervention had been randomized to one of the conditions.

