Randomization will be managed through an outside independent randomization service provided by the Perry Point Cooperative Studies Coordinating Center (PPCSPCC). The PPCSPCC has designed and developed a centralized, automated telephone system to randomize subjects into clinical trials. Study sites access the system using a pre-specified phone number and respond to a series of prompts regarding the subjects' eligibility. After the system verifies subject eligibility, it assigns each subject a treatment assignment. Randomizations can be done 24 hours a day, 7 days a week. Following each randomization, a fax notification is automatically sent to the site and others as needed. The system has also been programmed to send summary reports on a weekly basis.

This methodology does allow for the intervention groups to become slightly unbalanced during the trial within a CTP. With this methodology the group assignments may become predictable toward the end of recruitment to individuals familiar with the randomization scheme. This predictability could threaten the integrity of the randomization if potential participants could manipulate which condition they ended up in by when they enrolled in the study. We will minimize this potential problem by not informing participants of the total number being recruited, thus they will not know when recruiting is near its end when group assignment might be predictable if they knew the number of participants already recruited and to which conditions previous cohorts had been assigned. Another concern with predictability of assignment is with the research assistants as they are conducting initial baseline assessments. The research assistants will be instructed to not speculate/predict with the participants which condition a participant is likely to be assigned to prevent participant bias. In addition the research assistants will be kept blind to the blocked nature of the randomization. Thus from their perspective each cohort's randomization should be independent from previous condition assignments. Since the primary outcome measure is going to be obtained by the ACASI method, it is unlikely any bias the research assistant might have related to predictability of condition assignment would affect the collection of this crucial data.

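### Cohorts are randomised within CTP, but the model in 11.6 (and 11.7) omits CTP; if the GEE clusters on cohort, the test is mildly conservative and gives up one to two points of power

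*Protocol*

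**What the plan says.** Protocol 11.3 describes a stratified cluster-randomised design in which the stratum is the participating CTP and the cluster is the cohort of 3 to 8 men. Section 6.3.1 puts this into practice: "Separate block randomization schedules will be developed for each CTP with the assumption that 6 cohorts will eventually be randomized". Depending on recruitment, further cohorts follow from a new block. Where 35 or more men have already been recruited, a single extra cohort is "randomly assigned to one of the conditions independent of previous cohort assignments in that CTP". The same section accepts the consequence: "This methodology does allow for the intervention groups to become slightly unbalanced during the trial within a CTP".

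In 11.6, because the data have two hierarchical levels, "we will apply a marginal semi-parametric regression model to analyze the primary outcome". Model (1) is then written out in full: arm, time, arm by time, and the baseline count. After the baseline count, "The other two covariates we plan to include in the model are" an indicator of non-monogamy and years of stimulant use. There is no term for CTP or for treatment modality. Section 11.7 carries the same covariates into the logistic model for the dichotomous secondary outcomes. Estimation is by standard GEE, with neither the clustering unit nor the working correlation named.

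**The concern.** An analysis should normally carry the factor by which randomisation was stratified. Stratifying by CTP makes differences between clinics largely cancel from the treatment contrast. An analysis that does not know about CTP can leave those differences in the estimated error. The standard error is then larger than the true sampling variability, the test rejects too rarely under the null, and power is lost. Adjusting for CTP also removes whatever site difference enters by chance when the arms are unequal within a clinic.

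This is not a detail left for a later document. The protocol fixes the equation and its covariates, and the design's own stratum is not among them.

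**Working it through.** **The plan's own figure.** Section 11.3 uses m = 2(z₁ + z₂)²{1 + (I − 1)ρ}/(IΔ²). With I = 8, ρ = 0.01, Δ = 0.29:

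- m = 2 × 2.80² × 1.07 / (8 × 0.0841) = 16.78 / 0.6728 = 24.94, rounded up to 25 cohorts per condition. This reproduces.
- The formula carries the full design effect and takes no credit for stratification.

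**Inputs for the check.**

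- 14 CTPs with 6 cohorts each (6.3.1, 11.4): 84 cohorts, 42 per arm.
- 560 enrolled: 560/84 = 6.67 men per cohort. With 10% attrition: 504/84 = 6.0.
- Effect 0.29 SD, two-sided 5% (11.3).
- Site ICC ρₛ = 0.01 and 0.02, the two values in 11.3.
- Extra within-cohort ICC ρ_c = 0.01. This is an assumption. The protocol's equal-correlation structure corresponds to ρ_c = 0.
- Linear model of 11.3, one time point, equal cohort sizes, normal approximation.

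**Formulas, if the robust variance clusters on cohort and CTP is not in the model.**

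- Variance of a cohort mean as estimated: E = [1 + (I − 1)(ρₛ + ρ_c)]/I.
- Variance that matters for the within-site contrast: W = E − ρₛ.
- Estimated SE = √(2E/42); true SD = √(2W/42).
- Type I error = 2Φ(−1.96 × SE/SD).
- Power without CTP = Φ((0.29 − 1.96 × SE)/SD); with CTP = Φ(0.29/SD − 1.96).

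**Worked at ρₛ = 0.01, I = 6.**

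- E = 1.10/6 = 0.1833, so SE = 0.0934. W = 0.1733, so SD = 0.0909.
- SE/SD = 1.03; type I error = 2Φ(−2.016) = 4.4%.
- Power = Φ(1.176) = 88.0% without CTP and Φ(1.232) = 89.1% with it.

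**Results.** The SE ratio uses I = 6.67; the rest uses I = 6.

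| Site ICC | SE too large by | Type I error | Power without CTP | Power with CTP |
|---|---|---|---|---|
| 0.01 | 3% | 4.4% | 88.0% | 89.1% |
| 0.02 | 6% | 3.8% | 87.2% | 89.4% |
| 0.05 (assumed) | 15% | 2.5% | 84.6% | 90.2% |
| 0.10 (assumed) | 30% | 1.2% | 79.8% | 91.6% |

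The SE ratio hardly depends on ρ_c. With ρ_c = 0 and I = 6 it is √(0.1750/0.1650) = 1.03 at ρₛ = 0.01 and √(0.1833/0.1633) = 1.06 at 0.02.

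**Imbalance within sites.** The formulas above assume balance within each site, so imbalance was checked separately. Allocations following the 6.3.1 rules were simulated: 14 CTPs, cohorts of 3 to 8, 400 allocations per scenario, about 594 to 605 men, no attrition.

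- The share of men in one arm within a CTP differs from one half by 0.03 to 0.05 on average, with a 95th percentile of about 0.09 to 0.12.
- At site ICC 0.01 to 0.02, the part of the contrast due to site differences has SD 0.004 to 0.010. The upper end is about 3% of 0.29.
- The true SD of the contrast is 0.081 to 0.082 with or without CTP in the model (variance ratio 0.99 to 1.00).
- The variance estimated by clustering on cohort alone exceeds the CTP-adjusted variance by 4 to 14%. That is 2 to 7% on the SE, in line with the table.
- An exchangeable site-level correlation without a CTP term gives essentially the efficiency of the fixed-CTP model.

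**The case against.** The strongest reply is that 11.6 does not say that the GEE clusters on cohort. The only correlation structure written out, in 11.3, is indexed by CTP and gives any two men in the same CTP the same correlation, and 11.3 introduces it because the analysis will use GEE. If the analysis follows that structure, nearly all of the efficiency is recovered without a CTP term. This stands, and it makes the loss conditional. It does not remove the case for action: 11.3 also names the cohort as the cluster, and a sandwich variance clustered on CTP would rest on only 14 clusters.

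A second reply is that the large losses need a site ICC of 0.05 to 0.10. That also stands. The documents give no site-level variance, and 11.3 assumes an ICC of at most 0.01, with 0.02 as a sensitivity value. Section 5.1 does seek clinics that differ in ethnicity, region and primary drug, so a higher value cannot be excluded. The baseline count in model (1) would absorb part of any such difference, which the table ignores.

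A third reply is that the planned power does not depend on the gain from stratification. This is correct: the 11.3 formula never counted it, and the error is on the conservative side.

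A reader might infer that the stratification is wasted outright, or that site differences bias the treatment effect when arms are unequal within a clinic. The documents support neither. The first depends on an unstated clustering unit. The second is chance variation, negligible at the protocol's ICC values, provided that each cohort has the same chance of either arm.

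**Conclusion.** The point holds as a modest improvement to the analysis. Randomisation is stratified by CTP, and the models written out in 11.6 and 11.7 leave CTP out. If the GEE clusters on cohort, the cost at site ICC 0.01 to 0.02 is about one to two points of power and a type I error somewhat below 5%. The cost grows materially only at a site ICC of 0.05 to 0.10, which is an assumption without a source in the documents. If the GEE clusters on CTP with an exchangeable correlation, most of the efficiency returns, but the robust variance then relies on 14 clusters. The protocol's 80% power claim is not contradicted. The figures rest on the linear approximation of 11.3, not on the log-link count model, and on six equal cohorts per CTP. Low to moderate weight.

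**What to change.** In 11.6, add CTP to model (1) as a fixed effect. Its 13 indicators also absorb methadone versus drug-free treatment. Name the cohort as the GEE cluster, with a small-sample-corrected robust variance. Adding CTP under the log link raises no non-collapsibility problem for the treatment rate ratio.

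In 11.7, treat the continuous outcomes in the same way. For the logistic models, CTP indicators change the target from a marginal odds ratio to one conditional on site. Either include CTP and say so, or fit with CTP and standardise back to a marginal effect.

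A second-best alternative is to leave CTP out and state that the GEE clusters on CTP with an exchangeable working correlation, again with a small-sample correction because there are only 14 CTPs.

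The cost is a few sentences in 11.6 and 11.7, and 13 degrees of freedom out of about 500 participants. Sample size, randomisation and data collection are unchanged.
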